Table 2:	Treatment drugs	23
Table 3:	Pembrolizumab infusion reaction dose modification and treatment guidelines	25
Table 4:	Dose modification and toxicity management guidelines for immune-related AEs associated with pembrolizumab	34

ABBREVIATIONS

AE	Adverse Event
ALT	Alanine Aminotransferase
ALC	Absolute Lymphocyte Count
ALK	Anaplastic Lymphoma Kinase
AST	Aspartate Aminotransferase
BUN	Blood Urea Nitrogen
CBC	Complete Blood Count
CMP	Comprehensive Metabolic Panel
CR	Complete Response
CT	Computed Tomography
CTCAE	Common Terminology Criteria for Adverse Events
DEX	Dexamethasone
DLT	Dose Limiting Toxicity
DSMC	Data and Safety Monitoring Committee
ECI	Events of Clinical Interest
EGFR	Epidermal Growth Factor Receptor
ERC	Ethics Review Committee
GCP	Good Clinical Practice
H&P	History & Physical Exam
IHC	Immunohistochemistry
IRB	Institutional Review Board
irRECIST	Immune Response RECIST
IV (or iv)	Intravenously
MTD	Maximum Tolerated Dose
NCI	National Cancer Institute
NSCLC	Non-small cell lung cancer
ORR	Objective Response Rate
OS	Overall Survival
PBMCs	Peripheral Blood Mononuclear Cells
PD	Progressive Disease
PD-1	Programmed Cell Death Protein 1
PD-L1	Programmed Death-Ligand 1
PFS	Progression Free Survival
PI	Principal Investigator
PO	per os/by mouth/orally
PR	Partial Response

RECIST v1.1	Response Evaluation Criteria in Solid Tumors version 1.1
SAE	Serious Adverse Event
SD	Stable Disease
TEAE	Treatment-emergent Adverse Event
TSH	Thyroid Stimulating Hormone
WBC	White Blood Cells

1.0 TRIAL SUMMARY

Abbreviated Title	Induction of Senescence using Dexamethasone to Re-sensitize NSCLC to Anti-PD1 Therapy
Trial Phase	II
Trial Type	Interventional
Study Centers	VA Ann Arbor Healthcare System
Hypothesis	Pre-treatment of NSCLC with dexamethasone followed by pembrolizumab will result in induction of senescence with production of SASP and immune activation markers. Senescence will result in improved response to pembrolizumab.
Objectives	
Primary:
 
 - To determine whether dexamethasone induces senescence in >60% of patients with stage IV NSCLC who have progressed after initial immunotherapy 
Secondary:
 
 - In patients whose NSCLC has progressed on first line immunotherapy, determine the pre-treatment Dexamethasone duration needed to induce ORR to pembrolizumab of >33% - Determine ORR to pembrolizumab assessed by FDG PET - Determine the relationship between sensitivity to Dexamethasone and ORR using pre- and post-FLT PET and FDG PET scans respectively. - To evaluate response based on immune-related RECIST (ir-RECIST) criteria and compare to response rate as evaluated by RECIST v1.1. 
Exploratory:
 
 - Determine SASP and activation of T and NK cells, measured in peripheral blood. - Functional characterization, including activation markers and intracellular cytokine profile, of immune cell subsets will be evaluated by multi-parametric flow cytometry.
Type of control	Historical controls of patients treated with docetaxel treatment whose FLTPET response was 30% and overall response rate was $\leq 7\%$.
Study drugs: dose and administration	
Dexamethasone cohorts, PO, 4mg BID given for 7 or 10 or 13 days (followed by taper over 2-4 days and 3 day wash out) prior to first dose of pembrolizumab, followed by DEX 4mg BID for 7 or 10 or 13 days (followed by taper over 2-4 days and 3 day wash out) days prior to subsequent pembrolizumab x 3 cycles.
 
Cohort 1 & 2: Pembrolizumab, IV, 200mg on day 1 of a 21-day cycle
 
Cohort 3: Pembrolizumab, IV, 200mg on day 1 of a 28-day

Duration of administration	12 weeks
Inclusion Criteria	
 • Stage IIIA/B following CRT and durvalumab or Stage IV NSCLC whose tumors do not have a mutation in epidermal sensitizing growth factor (EGFR) or BRAF or rearrangements in ALK (anaplastic lymphoma kinase) or ROS-1 and have progressed on therapy with PD1 inhibitor

[figure not shown]
	
 • Presence of measurable disease according to RECIST v1.1 • ECOG performance status 0-2 No significant weight loss; >30% in 90-days • Adequate organ function defined as AST and ALT $\leq 2.5 \times$ ULN, bilirubin $\leq 1.5 \times$ ULN, and creatinine clearance ≥ 40 ml/min • Adequate hematologic parameters • Life expectancy of at least 6 months • Sufficient tissue sample of adequate quality for correlative studies
Exclusion Criteria	
 • Presence of significant comorbidities precluding participation in a clinical study as determined by investigator • Has active autoimmune disease that has required systemic treatment in the past 2 years • Baseline corticosteroid use at study entry • ECOG performance status 3-4 • Pregnancy or lactation
Number of trial subjects	21 to 39 patients
Statistical design	Simon's optimal design with lead in cohorts.
Estimated duration of trial	2 years from 1 st patient in, to last patient out
Estimated average length of treatment per patient	3 months

2.0 TRIAL DESIGN

2.1 Trial Design

This study is a small Phase II clinical trial designed as a single-arm two-stage study with Dexamethasone dose escalation cohorts (4mg BID on days 1-7, 1-10 or 1-13). The trial will include FLT-PET and FDG-PET imaging to measure tumor senescence to Dexamethasone and treatment response respectively, and also blood analysis for SASP and markers of immune activation. This study is to assess whether senescence induced by oral dexamethasone resensitizes NSCLC patients to intravenous pembrolizumab.

We will use a single arm phase II two-stage design with 3 Dex cohorts (4 mg bid, on Days 1-7, 1-10 and 1-14) to achieve 80% power at a 1-sided alpha 10% level. Each cohort will consist of 5 patients. On the basis of Simon's optimal design, the first cohort will be accrued in the first stage. If there are 3 or more "responses" occur among this cohort, 7 additional patients will be accrued and treated with the same Dex dose for a total of 12 patients; if 7 or more respond at this dose level, we will add 9 more patients for a total of 21 patients (with 20% drop out, n = 31). If no response is noted on FLTPET, 2nd cohort will open up with a 10 day fixed dose Dex and so on as depicted in Schema.

The secondary objective is to establish that the true ORR of Dex followed by pembrolizumab will be at least 33% ($p_1 = 0.33$) vs. docetaxel treatment (as the historical control) whose ORR is $\leq 7\%$ ($p_0 = 0.07$). The ORR will be assessed at a 12 week FDG PET scan. The required sample size for both lead-in FLTPET response and phase 2 studies will range 21 to 31 patients. As secondary objectives, we will explore associations of the change in FLT-PET with ORR assessed by FDG-PET, level of plasma SASP, and immune cell activation. The change in FLT-PET will be compared by ORR using an unpaired t-test and the associations with the level of plasma SASP and immune cell activation will be examined by a correlation analysis. The power is not formally justified because these are exploratory. The patients will be assessed starting with a standard of care FDG-PET within 28-days of 1st dose of dexamethasone along with FLT-PET at baseline (Day 0) and after the last dose of dexamethasone. Response will be assessed through FDG-PET at 12 weeks and with CT imaging every 3 months thereafter (standard of care) until progression. Blood samples for T/NK cell counts, SASP including cytokines and chemokines, and immune cell subsets will be collected. The study will use Response Evaluation Criteria in Solid Tumors version 1.1 (RECIST v1.1) for disease evaluation. Adverse event (AE) monitoring will occur prior to each cycle (21 days) and events will be graded according to the NCI Common Terminology Criteria for Adverse Events (CTCAE) version 4.0. Patients will continue on trial until confirmed progression as defined by RECIST v1.1, develops unacceptable toxicity or intercurrent illness that prevents further administration of treatment, withdrawal from study, removal by the investigator, becomes pregnant, demonstrates noncompliance with trial requirements, or has received 24 months of treatment with pembrolizumab. Patients may continue on treatment despite RECIST v1.1-defined progression if the subject is felt to be continuing to derive clinical benefit as determined by the investigator. Additional information including the irRC

[figure not shown]
(immune-related response criteria) may be used by the investigator in deciding continuing treatment beyond RECIST v1.1-defined progression.

At the end of treatment, all patients will continue to be followed for a minimum of 30 days for AE monitoring. Subjects will have post-treatment follow-up for disease status, including initiation of non-study cancer therapy until death, withdrawal of consent, or becoming lost to follow-up.

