11.0 STATISTICAL ANALYSIS PLAN

11.1 Statistical Design (see page 10 for Schema)

In the first stage, three DEX escalation cohorts will be evaluated sequentially from Cohort A to Cohort C until two or more patients have the FLT-PET response (i.e., \geq 30% reduction in FLT-PET uptake in at least one target lesion) and, otherwise, the trial will be terminated due to futility. When a lead-in cohort has two or more FLT-PET responses, this lead-in cohort will be considered the optimal DEX duration and the primary endpoint will be evaluated in the following second and third stages using this optimal DEX duration. That is, after the optimal DEX duration is decided in the first stage, six additional patients will be enrolled in the second stage with the same DEX duration as the associated cohort. If four or less patients respond among 11 patients, the trial will be terminated. Otherwise, 10 additional patients will be enrolled in the third stage. The null hypothesis ($p_0 = 30\%$) will be rejected if 10 or more FLT-PET responses are observed in 21 patients. This design yields a 1-sided type I error rate of 5% and power of 80% when the true FLT-PET response rate is 60% (i.e., $p_1 = 60\%$). The minimum sample size will be 11 patients when Cohort A becomes the optimal duration and the trial is terminated at the end of the second stage. The maximum sample size will be 31 patients when Cohort C becomes the optimal duration and the patients are enrolled into the third stage.

We will also explore the associations between the FLT-PET response and the changes in senescence associated secretory proteins (SASP) and lymphocyte, phenotypic and functional markers (LPFM), (ii) monitor the changes and trajectories in SASP and LPFM, and (iii) explore the association between the FLT-PET response and GR expression at cycle 0. The expression levels of SASP and LPFM/GR will be measured using plasma and tissue samples,

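### Sections 2.1 and 11.1 set incompatible rules for the primary FLT-PET decision; the Section 2.1 gates hold power to 56% to 78.9% against a stated 80%, and its n = 31 is not a 20% drop-out figure

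*Combined protocol and SAP*

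**What the plan says.** Section 2.1 describes a two-stage design based on Simon's optimal design, "to achieve 80% power at a 1-sided alpha 10% level". Each cohort has 5 patients. With 3 or more responders in the first cohort, "7 additional patients will be accrued and treated with the same Dex dose for a total of 12 patients; if 7 or more respond", 9 more are added "for a total of 21 patients (with 20% drop out, n = 31"). On escalation it says: "If no response is noted on FLTPET, 2nd cohort will open up". The text gives no action for 1 or 2 responders of 5 and no final rejection count. It refers to a schema that is not visible in the copy reviewed.

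Section 11.1 runs the cohorts in sequence "until two or more patients have the FLT-PET response", so 0 or 1 of 5 opens the next. Six patients are then added: "If four or less patients respond among 11 patients, the trial will be terminated". Otherwise 10 more are added, and the 30% null "will be rejected if 10 or more FLT-PET responses are observed in 21 patients". On operating characteristics: "This design yields a 1-sided type I error rate of 5% and power of 80"% at a true rate of 60%. In this section 31 is the maximum when Cohort C is selected.

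Section 11.2 calls the design three-stage and gives 39 as the maximum with 20% drop-out. Section 11.4 calls it two-stage. The synopsis gives 21 to 39 patients.

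**The concern.** Both sections are current text, and they direct different actions on the same data.

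- **2 of 5 responders:** Section 11.1 selects that duration and expands it. Section 2.1 does not expand it, and its text does not say what happens next.
- **5 of 11 responders:** Section 11.1 goes on to 21. Under Section 2.1 the twelfth patient can bring the count to 6 of 12 at most, short of 7, so that duration would not go on.
- **Alpha:** the nominal level is 10% in one section and 5% in the other.

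In a single-arm, open-label trial the primary claim rests entirely on prespecified counts and an alpha. Two rule sets leave open which duration is carried forward, how many patients receive it, and by what standard the result is judged. That choice could be made after the data are seen. A second problem is that the Section 2.1 gates look too strict for the 80% power claimed for them, and its drop-out figure does not follow from 21.

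**Working it through.** **Inputs.** p0 = 30% (synopsis, Sections 11.1 and 11.4) and p1 = 60% (Sections 11.1 and 11.4). Section 2.1 states neither for FLT-PET, so they are carried over. All results are exact binomial sums.

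**Section 11.1, reproducing its own figures (thresholds 2/5, 5/11, 10/21, one cohort).**

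| True rate | Pass 2/5 | Pass 2/5 and 5/11 | Reject at 10/21 |
|---|---|---|---|
| 30% | 0.4718 | 0.1831 | 0.0491 |
| 60% | 0.9130 | 0.8565 | 0.8218 |

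The stated 5% and 80% are met for one cohort taken alone. A failed lead-in (0 or 1 of 5) gives another chance. With all three durations at 30%, P(0 or 1 of 5) = 1 − 0.4718 = 0.5282, and the overall type I error is 0.0491 × (1 + 0.5282 + 0.5282²) = 0.0888. With all three at 60%, power is 0.8996.

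**Section 2.1 (thresholds 3/5, 7/12).** With no final count stated, the chance of passing both gates is an upper bound on power. At 60%:

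- P(3 or more of 5) = 0.3456 + 0.2592 + 0.0778 = 0.6826.
- P(both gates) = 0.3456 × P(Y ≥ 4) + 0.2592 × P(Y ≥ 3) + 0.0778 × P(Y ≥ 2), where Y is binomial(7, 0.6). This is 0.3456 × 0.7102 + 0.2592 × 0.9037 + 0.0778 × 0.9812 = 0.5560.
- Three cohorts, next opened only on 0 of 5 as written (P(0 of 5) = 0.01024): 0.5560 × (1 + 0.01024 + 0.01024²) = 0.5617.
- Three cohorts, next opened on any 0 to 2 of 5 (probability 1 − 0.6826 = 0.3174), all durations at 60%: 0.5560 × (1 + 0.3174 + 0.3174²) = 0.7885.
- With a 10/21 final count borrowed from Section 11.1, the three figures become 0.5514, 0.5571 and 0.7819.

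At 30%, the chances of passing both gates on the same three readings are 2.8%, 3.4% and 7.2%. These are upper bounds on the type I error.

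**How often the sections part.** P(exactly 2 of 5) is 0.2304 at 60% and 0.3087 at 30%. Any path that passes both Section 2.1 gates also passes the first two of Section 11.1. So at 60% the two rules differ on going to 21 patients with probability 0.8565 − 0.5560 = 0.3005 for one cohort.

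**Drop-out.** 21/0.8 = 26.25, so 27 (21 × 1.2 = 25.2, so 26, by the cruder method). Neither is 31. In Section 11.1, 31 = 21 + 5 + 5, before drop-out; 31/0.8 = 38.75, so 39, which matches Section 11.2 and the synopsis. Going from 21 to 31 would imply 1 − 21/31 = 32% drop-out.

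**Optional final count of 11/21 with the Section 11.1 gates.** One cohort: alpha 0.0219, power 0.7626. Three lead-in chances: alpha 0.0395; power 0.8348 if all durations are at 60%.

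**The case against.** Section 11 is the titled analysis plan, it alone gives a complete rule with a final count, and the synopsis total matches it, so the intended design can be guessed. This points to the likely direction of the correction but does not remove the conflict: Section 2.1 still directs different enrolment, and Section 11 disagrees with itself on the number of stages. The stage label alone is a small matter, since a lead-in plus two stages could be counted either way.

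The power shortfall is conditional. Section 2.1 gives no FLT-PET rates, and the unseen schema may settle the case of 1 or 2 of 5. The 78.9% is about one point below 80%, so the clear shortfall belongs to the literal escalation wording. These limits stand. If a cohort that fails at 12 patients also opened the next duration, the chance of passing would be 1 − (1 − 0.5560)³ = 91.2%. The text does not state that rule, and it could need 12 + 12 + 21 = 45 patients, above both 31 and 39.

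The two-fold difference in alpha is between nominal levels. The Section 2.1 gates are in fact the stricter: at most 2.8% type I error for one cohort, against 4.9% under Section 11.1. That is correct, and it means the stated 10% does not describe those gates either. No schema can make 3 of 5 equal 2 of 5, or 12 equal 11.

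**Conclusion.** The concern holds, and it needs to be settled before the first cohort is read. The conflict in gates, stage sizes, escalation trigger and nominal alpha is on the page and needs no assumption. It affects a first cohort with probability 23.0% to 30.9% through the 2-of-5 result alone. At 30% and 60%, the Section 2.1 rule falls about 24 points short of its stated power as literally written and about one point short on the wider escalation reading; the latter also assumes a 60% response at every duration. The Section 11.1 rule is the only one in the text that delivers its stated figures, and it does so for one cohort only. Its 8.9% over three chances assumes that all three durations are at 30%. The 31 in Section 2.1 is a mislabelled Cohort C total.

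**What to change.** Reconcile Sections 1, 2.1, 11.1, 11.2, 11.4 and the schema to one set of gates, stage sizes, cohort-opening rule, stage label and alpha. State the action for every count from 0 to 5. Which cohort-opening rule applies is for the sponsor to settle.

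If the Section 11.1 gates are kept, say that the 5% applies to one cohort taken alone and report about 8.9% over three lead-in chances. If 5% is meant for the whole trial, a final count of 11 of 21 gives 4.0%.

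Remove 31 as a drop-out figure. Label the sample size as 21 to 31 evaluable at full accrual, up to 39 with 20% drop-out, with 11 as the minimum when Cohort A is selected and the trial stops at the second stage.

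Keeping the Section 11.1 gates costs wording in the protocol and schema, with no extra patients or procedures, and a less favourable stated alpha. Moving to 11 of 21 changes the decision rule itself and lowers single-cohort power to 76.3%, below the planned 80% (83.5% if all three durations are at 60%).

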11.2 Sample Size Justification

The clinical trial is a single arm phase II intervention trial in Veterans as second line therapy, after progression on initial chemo-immunotherapy or immunotherapy for NSCLC. The enrolled patient will be in the study for 3 months and will then be followed for up to 2 years. We currently see at least 2-3 patients per month who will satisfy eligibility criteria and thus

the enrollment will be completed within 2 years (min 21 and max 39 patients). A sample size of 21 patients will not be powered for all the comparisons. But the data information obtained from this study will provide us preliminary information to design a more definitive study

The sample size was justified based on the primary objective. The FLT-PET response will be evaluated using a Phase II single-arm three-stage design with three lead-in efficacy (futility) cohorts. The sample size was estimated to achieve 80% power with a 1-sided 5% type I error rate and the estimated sample size is varied according to the selected optimal duration, which ranges from 21 patients (when Cohort A is optimal) to 31 patients (when Cohort C is optimal). Considering up to 20% drop-out rate, the required sample size will be between 21 patients (i.e., no drop-out with Cohort A as the optimal duration) and 39 patients (i.e., 20% drop-out with Cohort C as the optimal duration). For the secondary objective, the use of 21 patients (when the FLT-PET response trial enters the third stage) will allow us to achieve 87% power when the true ORR is 33% with a 1-sided type I error rate of 5%. We expect that the accrual rate will be at least 35 eligible and evaluable patients per year.

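### Section 2.1 labels 31 as 21 patients plus 20% drop-out (it should be 27), and the synopsis and Section 11.2 give a minimum of 21 without noting that Section 11.1 allows the trial to end at 11, 15 or 16

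*Combined protocol and SAP*

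**What the plan says.** Section 2.1 sets the lead-in size ("Each cohort will consist of 5 patients") and builds the selected cohort up through 12 to 21 patients. It attaches a drop-out allowance to that 21: "with 20% drop out, n = 31".

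Section 11.1 describes the design in more detail. Cohorts A to C are tested in turn "until two or more patients have the FLT-PET response"; "otherwise, the trial will be terminated due to futility". A cohort that passes gains 6 patients, making 11. The trial stops if 4 or fewer of the 11 respond; if not, 10 more are added, making 21. The same section states: "The minimum sample size will be 11 patients when Cohort A becomes the optimal duration" and the trial stops after the second stage. It gives 31 as the maximum, for Cohort C selected and the third stage filled, and mentions no drop-out there.

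Section 11.2 gives "min 21 and max 39 patients", and the synopsis (Section 1.0) gives "21 to 39 patients". Section 11.2 also explains its limits: 21 is Cohort A with no drop-out, and 39 is Cohort C with 20% drop-out. Sections 2.1 and 11.5 give a required range of 21 to 31.

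**The concern.** Two things do not fit. First, the same 31 is a figure after drop-out in Section 2.1 and a figure before drop-out in Sections 11.1 and 11.2. Both cannot be right, and no usual drop-out adjustment takes 21 to 31. Second, the lower limit is 21 in two places and 11 in a third, and the stopping rules produce other totals below 21 that are not stated anywhere.

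The enrolment range supports the two-year accrual statement in Section 11.2, and under Section 13.4 the monitoring committee reviews enrolment against expectation. A range that leaves out planned early stops, or a Cohort A target of 31 in place of 27, is a poor reference for either purpose.

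**Working it through.** **Inputs.** Lead-in cohorts of 5 (Section 2.1; also implied by 11 − 6 in Section 11.1). Pass the lead-in with at least 2 of 5, continue past stage 2 with at least 5 of 11, full size 21, up to three cohorts in sequence (Section 11.1). Drop-out 20% (Sections 2.1 and 11.2). Response rates 30% (null) and 60% (alternative).

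**The plan's own maximum.** Two failed lead-in cohorts plus a full third: 5 + 5 + 21 = 31, as in Section 11.1. Inflated as N/(1 − d): 31/0.8 = 38.75, so 39, as in Section 11.2. Both figures reproduce, and they show which inflation method the plan uses.

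**The figure in Section 2.1.** The same method on 21: 21/0.8 = 26.25, so **27**. The cruder 21 × 1.2 = 25.2 gives 26. To get 31 from 21, drop-out would have to be 1 − 21/31 = 32%. The 31 is therefore the Cohort C total before drop-out under the wrong label.

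**Possible totals under Section 11.1, before drop-out.** Write p for the response rate, taken as equal in all cohorts.

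- Pass the lead-in: P(X ≥ 2 of 5) = 0.4718 at 30% and 0.9130 at 60%. The chance of failing it, f, is 0.5282 or 0.0870.
- Pass, then stop at stage 2: s = Σ P(X = x of 5) × P(Y ≤ 4 − x of 6) over x = 2, 3, 4.
  - At 30%: 0.3087 × 0.7443 + 0.1323 × 0.4202 + 0.02835 × 0.1176 = 0.2887.
  - At 60%: 0.2304 × 0.1792 + 0.3456 × 0.04096 + 0.2592 × 0.0041 = 0.0565.
- Pass, then reach stage 3: g = (1 − f) − s = 0.1831 or 0.8565.

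| Path | Total | Formula | At 30% | At 60% |
|---|---|---|---|---|
| Cohort A, stop at stage 2 | 5 + 6 = 11 | s | 0.2887 | 0.0565 |
| No cohort passes | 3 × 5 = 15 | f³ | 0.1474 | 0.0007 |
| Cohort B, stop at stage 2 | 5 + 11 = 16 | f·s | 0.1525 | 0.0049 |
| Cohort A, full | 21 | g | 0.1831 | 0.8565 |
| Cohort C, stop at stage 2 | 5 + 5 + 11 = 21 | f²·s | 0.0806 | 0.0004 |
| Cohort B, full | 5 + 21 = 26 | f·g | 0.0967 | 0.0745 |
| Cohort C, full | 5 + 5 + 21 = 31 | f²·g | 0.0511 | 0.0065 |

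The first three rows sum to **0.589 at 30%** and **0.062 at 60%**.

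**Could drop-out close the gap?** No. With 20% drop-out the three early stops become 11/0.8 = 13.75 (14), 15/0.8 = 18.75 (19) and 16/0.8 = 20, all still below 21.

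**The case against.** The strongest reply is that 21 and 11 are different quantities and that each is defined. Section 11.2 ties its 21 to the size needed for 80% power with Cohort A selected and no drop-out, which is a full-enrolment figure. Section 11.1 ties its 11 to an early stop. This reply largely stands: the second part is a labelling conflict and not an error in sizing. It does not remove the conflict, because the short range in Section 11.2 calls 21 the minimum and the synopsis gives 21 with no qualifier.

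A reader might infer that a proper futility stop at 11 or 15 would be taken for under-enrolment. The documents do not support that. Section 11.1 sets out both futility stops and the minimum of 11 directly before Section 11.2, and Section 2.1 itself makes expansion conditional on responses.

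A reader might also see a contradiction between 21 to 31 in Sections 2.1 and 11.5 and 21 to 39 elsewhere. Their upper limits agree once 31 is read as before drop-out and 39 as after it.

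Finally, Section 2.1 uses other thresholds and stage sizes (3 of 5, then 7 of 12, then 9 more), so the stops at 11, 15 and 16 belong to Section 11.1 only. That is true, but it does not rescue the 31, and a second-stage stop in the first cohort under Section 2.1 falls at 12, also below 21.

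**Conclusion.** The point holds as a minor correction to stated figures. The 31 in Section 2.1 is wrong as labelled: it should be 27 for Cohort A, or be described as the Cohort C maximum before drop-out. The unqualified minimum of 21 conflicts with the 11 in Section 11.1 and omits the possible totals of 15 and 16. Under the Section 11.1 rules the trial ends below 21 patients with probability about 59% at a 30% response rate and 6% at 60%. Those percentages count patients before drop-out and assume one response rate across the three durations. If longer dexamethasone changes the rate, the figures for later cohorts change.

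It would be going too far to infer that the trial is wrongly sized. The 21-patient decision rule does not use any of the mislabelled numbers, and the maximum of 39 is arithmetically correct. Nor does a total of 21 show that the third stage was completed: Cohort C stopping at stage 2 also gives 21, with probability about 8% at a 30% rate.

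**What to change.** - **Section 2.1:** replace 31 with 27 for Cohort A, or state that 31 is the Cohort C maximum before drop-out and 39 the maximum after it. Reconcile the stage sizes in the same paragraph (12, then 9 more) with those in Section 11.1 (11, then 10 more); changing the one number alone would leave the two sections describing different designs.
- **Synopsis and Section 11.2:** state that the total before drop-out is 11 to 31 depending on path (11, 15, 16, 21, 26 or 31), with up to 39 enrolled to allow for 20% drop-out.
- **Sections 2.1, 11.2 and 11.5:** label 21 to 31 as the full-enrolment totals for Cohorts A to C (21, 26 and 31) before drop-out. Do not say that 21 arises only if the third stage is completed.

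The cost is wording only for the sample-size figures. Reconciling the Section 2.1 stage sizes requires the sponsor to confirm which description is in force.
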